Clinical Study Protocol

ClinicalTrials.gov entry no.	NCT05029739
Version number	1.0
Date of ethical approval	July 13, 2021

A Mobile Intervention for Patients with Peripheral Artery Disease (I-PAD): a Prospective Randomized Open Blinded End-point (PROBE) study

I. BACKGROUND AND SIGNIFICANCE

Peripheral artery disease (PAD) is a highly prevalent atherosclerotic syndrome with an estimated global population burden of ~200 million people (1). Patients with PAD are at heightened risk for adverse cardiovascular and limb events and impaired quality of life (2). Cigarette smoking is the most important modifiable risk factor for PAD. Patients with PAD who smoke have higher disease progression rates, greater risk of complications, poor post-procedural outcomes, compromised functional status, and increased hospitalizations, accounting for a higher patient and societal burden (3).

A significant goal of PAD treatment includes risk factor modification and prevention of cardiovascular events. Guideline directed therapy includes cardioprotective pharmacotherapies (i.e., antiplatelet therapy; statins; and blood pressure control, preferably with angiotensin-converting enzyme inhibitors (ACE-I) or angiotensin receptor blockers (ARBs)), and lifestyle modification (i.e., changes in diet, physical activity, and smoking cessation) (2). Nevertheless, adherence to pharmacologic and lifestyle recommendations in PAD is uncertain (4). Effective non-pharmacologic therapies for PAD also exist, including smoking cessation, exercise support, and diet counseling (5). However, limited data is available on mobile applications offering digitally delivered lifestyle change support, including a structured exercise program and smoking cessation support (6). This study aims to digitally provide lifestyle change support, including a structured and PAD-focused lifestyle program and smoking cessation support via a mobile platform (Sidekick Health) with the primary aim to increase patients' walking ability and secondary aims to reduce smoking and improve medication adherence.

II. SPECIFIC AIM

The specific aim is to determine whether a 12-week digitally delivered behavior change intervention for patients with peripheral artery disease increases walking ability, reduces smoking, improves quality of life and improves medication adherence. A follow-up visit after 12 months will be planned, to assess longer term effect on outcomes and healthcare cost.

Hypotheses

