- a) At the end of the 12 weeks, the interventional arm will reach a clinically meaningful change in walking ability, as compared to controls, measured by a change in the 6-MWT at twelve-week, and 12 months; the minimal clinically important difference (MCID) is defined as +12m (7).

- b) At the end of the 12 weeks, $\geq 15\%$ interventional treatment arm participants will give up smoking or have significantly reduced their daily smoking compared to less than $\leq 10\%$ in the control arm.
- c) At the end of the 12 weeks, $\geq 50\%$ of interventional treatment arm participants will improve their medication adherence from pre- until post-intervention as compared to $< 30\%$ in the control arm.
- d) Healthcare cost will be reduced at 12 month follow-up in the intervention arm.

III. METHODOLOGY

We will implement a randomized controlled study of a 12-week lifestyle intervention for patients with peripheral arterial disease, delivered via the digital platform Sidekick Health. Participants will be recruited and randomized in a 1:1 manner to the digitally delivered intervention + standard of care or standard of care only. The standard of care group will receive an information leaflet on important lifestyle factors for PAD and smoking cessation and medical adherence will be encouraged by the health care provider. The interventional arm will receive a digital program delivered to their mobile phone alongside standard of care. Replicating a real-life scenario a personalized approach will be applied in the interventional arm, especially regarding smokers. Therefore, two pathways are possible in the interventional arm in this trial, one for smokers who want assistance in smoking cessation (PAD-SC) and another for non-smokers or those who smoke and do not desire to quit (PAD-Reg). Patients will be followed up at 12 weeks. We aim to do a separate follow-up at twelve months. The primary outcome will be a change in pain-free and maximal walking ability, measured by the 6-minute walking test. Secondary outcomes will include smoking status change (in PAD-SC group as compared to the control arm), medication adherence and lifestyle changes (increased physical activity, changes in self-assessed stress/energy/sleep quality levels), health-related quality of life, and a reduced need for hospitalization or revascularization due to PAD at 12 months of follow up.

Subject selection

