Analyses will be performed according to the intention-to-treat principle and per-protocol analyses. Baseline characteristics and raw score questionnaire outcomes will be summarized as mean and SD for continuous measures and absolute numbers and percentages in each group. Changes in each outcome between baseline, post-intervention, and later a 12-month follow-up will be compared between and within the groups using t-tests or non-parametric statistical tests as appropriate. For the between-group differences, 95% Confidence Intervals will be reported. Correlations will be run to explore relationships between variables. For the primary outcome analyses, Ancovas or Mixed Anovas (repeated measures anovas) will be used, correcting for covariates that are significantly different between groups. The size of the change in HRQoL will be related to minimal important change values for the VascuQoL-6. It will be further assessed through effect size calculations (effect size=the difference in mean values between baseline and follow-up, divided by the SD at baseline). Cohen's criteria for interpreting effect sizes will be applied (small, 0.2–0.5; moderate, 0.5–0.8 and large, over 0.8). The a priori level for statistical significance will be set at a 2-sided $P < .05$.

V. RISKS AND DISCOMFORTS

We expect minimal to no risks and discomforts to be associated with this study. The lifestyle/behavioral change program is guideline-compliant for PAD patients and has

been reviewed by several medical doctors, behavioral scientists, and specialists in vascular surgery. Psychosocial risks will be minimal as well.

VI. POTENTIAL BENEFITS

Potential Benefits to Participating Individuals

The hope is that the intervention will increase participants' walking ability, reducing IC symptoms and prevent revascularization, empower participants to change their lifestyle and smoking patterns for the better, or that they will quit smoking altogether. Further, this intervention may also improve other patient-reported outcomes (e.g., reduce stress, improve sleep) without causing significant harm. Although the expected benefits are limited for patients that are allocated to usual care in the study, the enhanced follow-up at 12 weeks and 12 months may allow for a more careful evaluation and subsequent treatment of their condition following the end of study.

Potential Benefits to Society

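### Walking is the only named primary outcome, but the smoking, adherence, cost and quality-of-life claims share its uncorrected 5% level, with no testing sequence and no supportive label

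*Combined protocol and SAP*

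**What the plan says.** **Ranking.** Section I sets up the study "with the primary aim to increase patients' walking ability and secondary aims to reduce smoking and improve medication adherence". The Primary Outcomes list in section IV contains walking ability only; smoking, adherence, quality of life, cost and others are listed as secondary.

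**Claims.** The specific aim in section II asks whether the programme "increases walking ability, reduces smoking, improves quality of life and improves medication adherence". Hypotheses (a) to (d) then cover walking, smoking, adherence and cost. Hypotheses (b) and (c) carry numerical targets: at least 15% v at most 10% for smoking, and at least 50% v under 30% for adherence. Hypothesis (d) reads "Healthcare cost will be reduced at 12 month follow-up in the intervention arm". Quality of life appears in the aim but has no lettered hypothesis.

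**Testing.** Statistical Methods states: "Changes in each outcome between baseline, post-intervention, and later a 12-month follow-up will be compared between and within the groups". One level governs all of this: "The a priori level for statistical significance will be set at a 2-sided" P of .05. The section also promises 95% confidence intervals for between-group differences. It contains no order of testing, no adjustment, and no sentence on how to read a secondary result when walking is not significant.

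**The concern.** A primary label fixes which result decides the trial. It does not say what a P value of .04 on adherence means when walking shows nothing. As written, such a result could be reported as support for hypothesis (c) on the same footing as a positive walking result, and likewise for smoking or quality of life. The stated 5% applies to each test separately, not to the set of claims in the aim and hypotheses. At stake is a conclusion that the app works, resting on one secondary result among several.

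**Working it through.** **Inputs from the documents.** Two-sided level 0.05 (Statistical Methods). Five claims: walking, smoking, quality of life and adherence (specific aim), and cost (hypothesis d). Design: f = 0.15, alpha 0.05, power 0.80, correlation 0.25 between time points, 134 patients, 67 per arm (Subject enrollment).

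**Assumption.** The correlation r between test statistics is not given. I show 0, 0.3 and 0.5, equal for all pairs.

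**Step 1: the plan's own figure.** For a two-group, two-time-point interaction, the noncentrality is f² × N × m / (1 − r) = 0.0225 × 134 × 2 / 0.75 = 8.04. With 1 and 132 degrees of freedom this gives 80.4% power at 0.05, and 134 is the smallest even N that reaches 80%. The design therefore rests on one walking test at the full 0.05.

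**Step 2: chance of at least one P<.05 with no true effect.** Under independence this is 1 − 0.95^k in either direction and 1 − 0.975^k in the app's favour:

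- k = 5: 1 − 0.95^5 = 22.6%; 1 − 0.975^5 = 11.9%.
- k = 4 (without walking): 1 − 0.95^4 = 18.5%; 1 − 0.975^4 = 9.6%.

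With equal correlation r, the k statistics share a common normal component. The chance is one minus the average, over that component, of the k-th power of the conditional probability of staying inside the limit (1.96). Numerical integration gives:

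| Claims | Direction | r = 0 | r = 0.3 | r = 0.5 |
|---|---|---|---|---|
| 5 | either | 22.6% | 20.9% | 18.3% |
| 5 | in favour | 11.9% | 10.5% | 9.2% |
| 4 non-walking | either | 18.5% | 17.4% | 15.6% |
| 4 non-walking | in favour | 9.6% | 8.7% | 7.8% |

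The references for one test are 5% and 2.5%.

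**Step 3: a wider count, for illustration only.** Five outcomes compared in both arms (6MWT, VascuQoL-6, MMAS-8, smoking, readiness ladder) at two visits, plus cost, QALYs and hospitalisation/revascularisation, make 5 × 2 + 3 = 13. That gives 33% to 49% in either direction and 17% to 28% in favour over the same correlations. The in-app step, stress, energy and sleep measures are collected in the intervention arm only, so they add no between-arm test.

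**Step 4: the price of correction.** Splitting alpha equally over five claims (0.01 each) would cut walking power at 134 patients from 80.4% to 58.9%, and 198 patients would be needed for 80%. Testing walking first at 0.05 avoids that loss.

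For hypothesis (c) at 50% v 30%, 67 per arm, the pooled standard error is √(2 × 0.4 × 0.6 / 67) = 0.0846 and the unpooled one is √((0.25 + 0.21) / 67) = 0.0829. Power is Φ((0.20 − z × 0.0846) / 0.0829):

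- z = 1.960 (level 0.05): 66%.
- z = 2.394 (level 0.05/3 = 0.0167, strictest Holm step): 49%.
- Behind a walking gate with 80% power, if independent: 0.80 × 0.487 = 39%.

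**The case against.** The strongest reply is that the plan does rank its outcomes. Walking is the sole primary outcome and has its own models (ANCOVA or mixed ANOVA), formal completion is placed at 12 weeks, and 12 months is treated as a separate follow-up. **This stands.** A reader might infer that the outcomes have no order, or that the primary error rate is inflated by the secondaries. The documents do not support either: a single primary walking test has 5% error whatever the secondaries show. What is missing is a testing sequence and a status for the other results.

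A reader might also quote a chance of 17% to 49% for some significant result. Those ends measure different things: 17% is 13 comparisons in the app's favour at correlation 0.5, and 49% is 13 independent comparisons in either direction. The count of 13 is a reviewer's construction. The top rungs of the readiness ladder record having quit, hospital events feed hospital cost, and five outcomes are counted twice in the same patients. Cost and QALYs go to a separate cost-effectiveness analysis with no clearly specified P value.

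That last point also weakens cost as a fifth test, though hypothesis (d) is still worded as a claim. Similarly, P<.05 alone would not meet the numerical targets in (b) and (c), and quality of life is to be read against minimal important change values. These points soften the concern but leave the gap, because nothing says a significant secondary result is only supportive.

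Finally, formal error control over secondary outcomes can be seen as a reporting choice, and the promised confidence intervals help. That is fair, and it is why a plain supportive label is an acceptable remedy.

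**Conclusion.** The point holds for the wider set of claims, not for the primary test. With no true effect, the five claims carry about an 18% to 23% chance of at least one P<.05 (9% to 12% in the app's favour), and the four non-walking claims about 16% to 19% (8% to 10% in favour). The figures rest on one test per claim and on assumed correlations of 0 to 0.5; a higher correlation would lower them. The 13-comparison figures are not needed for the conclusion. This is a worthwhile and cheap improvement and does not invalidate the design. It presumes that walking is itself reduced to one test. The Methodology section gives "The primary outcome will be a change in pain-free and maximal walking ability, measured by the 6-minute walking test", and hypothesis (a) has it "measured by a change in the 6-MWT at twelve-week, and 12 months", so the walking measure and visit must be settled for the 5% to hold.

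**What to change.** In Statistical Methods, name the week-12 between-group comparison of the 6MWT, on one stated walking measure, as the single confirmatory test at two-sided 0.05. Then choose one of two routes:

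1. Report all secondary and 12-month comparisons as supportive estimates with 95% confidence intervals and no claim of confirmation.
2. If formal secondary claims are wanted, test week-12 smoking, adherence and VascuQoL-6 by Holm at 0.05, only if walking is significant. Report everything else as in route 1.

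The change needs a few sentences and no new data, and leaves the 134 patients and 80.4% walking power as they are.

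The cost falls on the secondary claims. Under route 2, power for hypothesis (c) at 50% v 30% drops from 66% to 49% at the strictest Holm step, and to about 39% once an independent walking gate with 80% power is counted. Under either route, hypothesis (d) and the 12-month part of (a) become estimates rather than tests, so their wording in section II should be changed to match.

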After recruitment, measurements and data collections will occur at each clinic by a experienced clinic or research nurse, as shown in table 2 and further detailed under section VIII. Furthermore, a 6-minute walking test will be administered by a trained clinic nurse at baseline, after 12 weeks and for a separate follow-up at 12 months. The American Thoracic Society protocol for the 6-minute walking test, modified for patients with intermittent claudication (IC), will be used. The 6MWT has excellent test-retest reliability for patients with IC. (8, 9). A central computerized procedure will randomly assign participants to treatment arms, stratified for study site and smoking status.

Intervention:

Participants will be instructed to download the SKH mobile app, and they will receive an access code to activate the PAD lifestyle change program. After the first week of the program, participants who smoke will be offered to incorporate smoking cessation support into their PAD program. These changes are minor and not intended to divide the intervention group in two but instead personalize the experience. Personalization of the program is essential for engagement and to deliver the most meaningful impact on clinical outcomes. The program aims to empower positive lifestyle change by gamification, altruistic rewards, and engaging content with relevant tasks or missions to be completed. Beyond this, all patients in the interventional arm will also receive standard of care as defined below for the control arm.

Participants in the intervention group will also be asked to do a separate and virtually delivered 6-minute walking test to validate the digital in-app 6MWT.

Control:

All patients in the control arm will receive best medical treatment including start or optimization of secondary preventive pharmacotherapy, smoking cessation advise and advise on modifiable risk factors. The control arm will also receive an information leaflet about relevant lifestyle modifications for PAD. After baseline measurements and data collection, there will be no scheduled visits by a health care provider until week 12.

Table 2. Timing of Proposed Data Collection and Instruments Used

Data collection/Instruments	Baseline	Post-Intervention (after week 12)	12-month follow-up
All participants (intervention and control)			
Demographic and Clinical/Medical Baseline Information (e.g., tobacco use, other risk factors, and comorbidities)	Yes	Yes	Yes
6-Minute Walking Test	Yes	Yes	Yes

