The hope is that this program will contribute to a healthier population. If the Sidekick PAD program proves efficient because it is highly scalable, it may alter the disease progression and improve millions' lives. The program may also positively impact the environment if participants quit smoking as cigarettes are a considerable environmental pollutant.

VII. MONITORING AND QUALITY ASSURANCE

SKH will regularly monitor study data accuracy and will guarantee safe study data storage. Furthermore, SKH will monitor and amend potential technical issues that hinder participants' accurate access to and using the smartphone application and its full functionality. As soon as the opportunity arises, the obtained data will be anonymized and removed from personal health information. All participants will be de-identified and assigned research subject IDs (e.g., participant 1). Only the study staff will have access to information that can link the subject IDs with the personal health information, saved on a secure, shared drive. Further, clinic staff/providers will report any adverse events using standard procedures.

VIII. VARIABLES TO BE COLLECTED

Demographic/clinical/anthropometric variables:

1. Age
2. Gender
3. Smoking status
4. Height
5. Weight

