6. BMI
7. Waist circumference
8. Ankle-brachial index (ABI)
9. Comorbidities (obesity, diabetes type 1 or 2, other CVD)
10. Relevant medications. Information on medical therapies will focus on medicines important for secondary prevention of PAD, will not collect specific dosing, and will be dichotomously (yes/no) categorized as follows:
 - a. Antihypertensive agent(s)
 - b. Antidiabetic agents (both peroral and injectables will be categorized into one single category)
 - c. Lipid lowering therapy (statins, ezetimibe and PCSK-9 inhibitors will be categorized into one single category)
 - d. Antiplatelet therapy
 - i. Single antiplatelet therapy
 - ii. Dual antiplatelet therapy
 - e. Anticoagulation therapy
 - i. Low dose rivaroxaban
 - ii. Therapeutic anticoagulation
11. Health literacy status
12. Educational level (primary school, high school, higher education)
13. Work status (working, unemployed, retired)

In-app activity collected:

Self-reported measurements	Age, gender, height, weight, sleep quality, stress level, energy level.
Logged items	Fruits, vegetables, nuts, and seeds consumed. Physical activity tasks. Stress reduction tasks. Food photos, diet improvement tasks.

Missions/tasks	Some involve in-app logging (see above), others not logged.
6 MWT in-app	A 6-minute walking test feature available in the SK app uses GPS outdoors, roughly assessing cardiorespiratory fitness.

Measurements and Questionnaires:

1. Protocol for a 6-minute walking test (see appendix A)
2. Vascular Quality of Life Questionnaire (VascuQoL-6)
3. A standard measurement of health status (EQ-5D-5L)
4. The European health literacy survey (HLS-EU-Q16 Swedish version)
5. Morisky Medication Adherence Scale (MMAS-8)
6. Readiness to quit smoking (The Contemplation Ladder)

IX. REFERENCES:

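### No visit asks either arm about adverse events and no by-arm safety summary is planned, so the harm count could be incomplete and differ by arm

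*Combined protocol and SAP*

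**What the plan says.** **Reporting rule.** Section VII (Monitoring and Quality Assurance) states that "clinic staff/providers will report any adverse events using standard procedures". The protocol gives no definition of an adverse event, form, reporting window or seriousness rule.

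**Contact.** Section III, Study procedures, says under Control: "After baseline measurements and data collection, there will be no scheduled visits by a health care provider until week 12". Under Intervention it says that "all patients in the interventional arm will also receive standard of care as defined below for the control arm". Table 2 has three time points for both arms: baseline, after week 12, and 12 months.

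**What is collected.** Table 2 repeats at every visit a row headed "Demographic and Clinical/Medical Baseline Information (e.g., tobacco use, other risk factors, and comorbidities"), together with the walk test, the questionnaires and, for smokers, the smoking measures. Neither Table 2 nor Section VIII lists adverse events. Section IV lists no safety outcome, and its Statistical Methods describe no safety analysis.

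**Partial routes.** The opening of Section III names PAD-related hospitalisation or revascularisation at 12 months as a secondary outcome, framed as a reduction. It is absent from the secondary outcomes in Section IV, from Table 2 and from Section VIII. Section IV uses hospital cost databases for the cost-effectiveness analysis.

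**Expectations.** Section V expects little or no risk. Section VI hopes that the programme may "reduce stress, improve sleep) without causing significant harm". Section I notes that "Patients with PAD are at heightened risk for adverse cardiovascular and limb events".

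**The concern.** Staff can report only what reaches them. A fall, chest symptoms or a foot wound in, say, week 5 would reach the clinic only if the patient made contact unprompted. At week 12 and at 12 months nothing in the data-collection schedule prompts the nurse to ask.

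The trial is open-label. Section IV asks for blinded evaluation of endpoints as far as possible, but adverse events are not an endpoint, so no stated safeguard covers how they are elicited. Staff may be more alert to exercise-related problems in the app arm, or app-arm patients may be less inclined to contact the clinic. The direction cannot be predicted, but either would make the counts non-comparable.

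The intervention includes a structured exercise programme, and its "walking test feature available in the SK app uses GPS outdoors". Readers will want to know whether harms differed between arms. Under the plan as written, few reports could mean few events or few questions.

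**Working it through.** **1. The plan's own figures.** The protocol gives no safety figure. The arm sizes come from Section III, Subject enrollment: 67 per arm evaluable (134 in total) and 155 to be recruited.

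- Check of 134: two-group, two-time-point repeated-measures interaction with f = 0.15, r = 0.25 and two-sided alpha 0.05. Noncentrality = f² × N × 2 / (1 − r) = 0.0225 × 134 × 2 / 0.75 = 8.04, with 1 and 132 degrees of freedom. Power is 0.804; at N = 132 it is 0.798. The 134 reproduces.
- Recruited per arm: 155 / 2 = 77.5, taken as 77.

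**2. Could an existing item pick up a harm between visits?**

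| Item | What it captures | Why it does not fill the gap |
|---|---|---|
| PAD hospitalisation or revascularisation (Section III) | Serious limb-related care by 12 months | No collection method; does not cover falls, injuries, cardiac events or foot wounds treated outside hospital |
| Comorbidities (Table 2; Section VIII, item 9) | Obesity, diabetes, other cardiovascular disease | A new diagnosis could be recorded, but not as a dated event |
| VascuQoL-6 | Previous two weeks | Does not ask about earlier events |
| EQ-5D-5L | Today | Does not ask about events |
| In-app items (Section VIII) | Sleep, stress, energy, diet and activity logs | No health-problem item; app arm only |
| Hospital cost databases (Section IV) | Cost per patient | Assigned to cost-effectiveness only |

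**3. What zero reports would show.** With n patients and no events, the one-sided 95% upper bound on the rate is 1 − 0.05^(1/n). If each event is captured with probability q, the bound on the true rate is that value divided by q. The protocol gives no q, so the values below 1 are assumptions.

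| n | q = 1 | q = 0.5 (assumed) |
|---|---|---|
| 67 | 1 − 0.05^(1/67) = 4.4% | 8.7% |
| 77 | 1 − 0.05^(1/77) = 3.8% | 7.6% |

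For a true rate of 5% (assumed) and n = 67, the chance of recording at least one event is 1 − (1 − 0.05q)^67: 97% at q = 1, 82% at q = 0.5 and 64% at q = 0.3.

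**4. Comparison of arms.** With true rates p_A and p_C and capture q_A and q_C, the expected ratio of recorded rates is (p_A × q_A) / (p_C × q_C). If the true rates are equal, this reduces to q_A / q_C, which says only who was asked or who volunteered. The protocol gives no basis for a value of either.

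**5. Is a formal test useful?** With 67 per arm and a two-sided 0.05 level, power is 19% for 10% against 5%, 49% for 15% against 5%, and 75% for 20% against 5% (rates assumed). A descriptive table with intervals is the realistic aim.

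**The case against.** The strongest reply is that Section VII does commit staff to report any adverse event. The procedures it refers to may exist outside this document and may include asking patients. This stands in part: a reader might infer that harms are recorded only by chance, and the text does not support that. What can be shown is that the procedures are undescribed and that nothing in the schedule or variable list solicits events. General reporting procedures would not by themselves supply an identical question in both arms or a by-arm table.

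Three further inferences go beyond the documents.

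- **That the protocol states no visits for the app arm before week 12.** The sentence stands under Control. For the app arm it follows from the shared standard of care and from Table 2, which shows no interim visit.
- **That the trial plans to conclude there is no significant harm.** The phrase in Section VI is a hope. No hypothesis, outcome or analysis commits to it.
- **That the participants are high-risk without qualification.** Section I describes PAD patients in general. Table 1 requires three months of stable disease and excludes critical limb ischaemia, prior amputation and other conditions that limit walking.

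It is also fair to say that the partial routes might show some limb or cardiac worsening, that the capture rates are assumed, and that the proposed question relies on recall and would not reach full capture either. None of this supplies a comparable question to both arms.

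**Conclusion.** The point holds as a cheap improvement. Apart from PAD hospitalisation or revascularisation, which has no stated collection method, harm capture rests on one sentence about undescribed procedures. The resulting count could be incomplete and could differ by arm for reasons unrelated to the intervention. A low count would therefore give little support to the expectation in Section V.

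The size is illustrative only: an upper bound of 4.4% to 3.8% after zero events in 67 to 77 app-arm patients with full capture, and about double that if half of events are captured. The size of any difference in capture between arms cannot be estimated from the documents.

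No primary or listed secondary analysis is affected, and the documents do not show that harms would go unreported. The conclusion assumes that no adverse-event form or questioning procedure exists outside the public document.

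**What to change.** Add one row to Table 2, under all participants, for adverse events at week 12 and 12 months. At these existing visits the nurse asks both arms the same short closed list covering the period since the last visit: falls or injury, cardiac events, limb or foot events, and other serious events. The questions come before allocation is discussed. Record the date, the seriousness, and whether the event occurred during walking or a walk test. Add the matching variables to Section VIII, and in Section IV a descriptive table of counts by randomised arm with confidence intervals.

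No step through the app is proposed, because Section VIII describes no in-app report of health problems and controls would lack that route.

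The cost is a few minutes per visit, one form and one table, with no added visits or staff. There are two downsides. Answers rely on recall, over 12 weeks at the first visit and about nine months at the second. More minor events will also be recorded, so the safety profile may look slightly less favourable.
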